8.2. Storage

The IMP will be stored in a securely locked cabinet or enclosure. Access will be limited to investigators and their designees. Neither investigators nor any designees may provide IMP to any subject not participating in this protocol.

The IMP will be stored at ambient conditions as per the clinical label on the IMP. The clinical site staff will ensure that the temperature log is maintained in the drug storage area and that the temperature is recorded at least once each working day.

8.3. Accountability

The investigator or designee must maintain an inventory record of IMP (including investigational, active control, or placebo) received, dispensed, administered, and returned.

8.4. Returns and Destruction

Upon completion or termination of the trial, all unused and/or partially used IMP must be returned to the sponsor or a designated agent.

All IMP returned to the sponsor must be accompanied by appropriate documentation and be identified by protocol number with trial site number on the outermost shipping container. Returned supplies should be in the original containers (eg, subject kits). The assigned trial monitor will facilitate the return of unused and/or partially used IMP.

8.5. Reporting of Product Quality Complaints (PQC)

A product quality complaint (PQC) is any written, electronic, or verbal communication by a healthcare professional, consumer, subject, medical representative, Competent Authority, regulatory agency, partner, affiliate or other third party that alleges deficiencies or dissatisfaction related to identity, quality, labeling, packaging, reliability, safety, durability, tampering, counterfeiting, theft, effectiveness or performance of a drug product or medical device after it is released for distribution. Examples include, but are not limited to, communications involving:

- Failure/malfunction of a product to meet any of its specifications
- Incorrect or missing labeling
- Packaging issues (eg, damaged, dirty, crushed, missing product)
- Blister defects (eg, missing, empty blisters)

Protocol 331-12-283

- Bottle defects (eg, under fill or overfill, no safety seal)
- Vial defects
- Product defect (eg, odor, chipped, broken, embossing illegible)
- Loss or theft of product

8.5.1. Eliciting and Reporting Product Quality Complaints

The investigator or designee must record all PQC's identified through any means from the receipt of the IMP from sponsor through and including reconciliation and up to destruction, including subject dosing. The investigator or designee must notify the sponsor (or sponsor's designee) within 24 hours of becoming aware of the PQC by e-mail or telephone and according to the procedure outlined below.

- Online: Send information required for reporting purposes (listed below) to PPD
- Phone: Rocky Mountain Call Center at PPD

Identification of a PQC by the subject should be reported to the site investigator, who should then follow one of the reporting mechanisms above.

8.5.2. Information Required for Reporting Purposes

- Description of compliant
- Reporter identification (eg, subject, investigator, site, etc.)
- Reporter contact information (eg, address, phone number, e-mail address)
- ID of material (product/compound name, coding)
- Clinical protocol reference (number and/or trial name)
- Dosage form/strength (if known)
- Pictures (if available)
- Availability for return

8.5.3. Return Process

It should be indicated during the report of the PQC if the IMP sample is available for return. If the complaint sample is available for return, return it in the product retrieval package, which will be provided by Otsuka America Pharmaceutical, Inc. Ethics, Quality and Compliance (OAPI-EQC). It should be documented in the site accountability record that a complaint sample for a dispensed kit has been forwarded to OAPI-EQC for complaint investigation.

Protocol 331-12-283

8.5.4. Assessment and Evaluation

Assessment and evaluation of PQC will be handled by the OAPI EQC-QM group.

9. Records Management

9.1. Source Documents

Source documents are defined as the results of original observations and activities of a clinical investigation. Source documents will include (but are not limited) to progress notes, electronic data, screening logs, and recorded data from automated instruments. All source documents pertaining to this trial will be maintained by the investigators.

Investigator(s)/institution(s) will permit trial-related monitoring, audits, IRB/IEC review, and regulatory inspection(s) by providing direct access to source data/documents by authorized persons as defined in the ICF.

9.2. Data Collection

During each subject's visit to the clinic, a clinician participating in the trial will record progress notes to document all significant observations. At a minimum, these notes will contain:

- Documentation of the informed consent process, including any revisions
- The date of the visit and the corresponding visit or day in the trial schedule
- General subject status remarks, including any significant medical findings. The severity, frequency, duration, action taken, and outcome of any AEs and the investigator's assessment of relationship to the IMP must also be recorded.
- Any changes in concomitant medications or dosages
- A general reference to the procedures completed
- The signature (or initials or other unique identifier) and date of each clinician (or designee) who made an entry in the progress notes

In addition, any contact with the subject or caregiver via telephone or other means that provides significant clinical information will also be documented in the progress notes as described above. Any changes to information in the trial progress notes and other source documents will be **initialed and dated on the day the change is made** by a site staff member authorized to make the change. Changes will be made by striking a single line through erroneous data (so as not to obliterate the original data), and clearly entering the correct data (eg, ~~wrong data~~ right data). If the reason for the change is not apparent, a brief explanation for the change will be written in the source documentation by the clinician.

Protocol 331-12-283

Information from the trial progress notes and other source documents will be data entered by investigative site personnel directly onto eCRFs in the sponsor's electronic data capture system.

9.3. File Management at the Trial Site

The investigator will ensure that the trial site file is maintained in accordance with Section 8 of the ICH GCP guideline and as required by applicable local regulations. The investigator/institution will take measures to prevent accidental or premature destruction of these documents.

9.4. Records Retention at the Trial Site

Regulatory requirements for the archival of records for this trial necessitate that participating investigators maintain detailed clinical data for the longest of the following 3 periods:

- A period of at least 2 years following the date on which approval to market the drug is obtained (or if IMP development is discontinued, the date regulatory authorities were notified of discontinuation).
- A period of at least 3 years after the sponsor notifies the investigator that the final report has been filed with regulatory authorities.
- Longer, region-specific storage requirements, if applicable.

The investigator must not dispose of any records relevant to this trial without either (1) written permission from the sponsor or (2) provision of an opportunity for sponsor to collect such records. The investigator will be responsible to maintain adequate and accurate electronic or hard copy source documents of all observations and data generated during this trial, including the eCRF data on the CD-ROM and any data clarification forms received from the sponsor or sponsor's designee. Such documentation is subject to inspection by the sponsor, sponsor's designee, and relevant regulatory agencies. If the investigator withdraws from the trial (eg, due to relocation or retirement), all trial-related records should be transferred to a mutually agreed-upon designee within a sponsor-specified time frame. Notice of such transfer will be given to the sponsor in writing.

Protocol 331-12-283

10. Quality Control and Quality Assurance

10.1. Monitoring

The sponsor has ethical, legal, and scientific obligations to follow this trial carefully in a detailed and orderly manner in accordance with established research principles, the ICH GCP guideline, and applicable regulatory requirements and local laws. As part of a concerted effort to fulfill these obligations (maintain current personal knowledge of the progress of the trial), the sponsor's monitors will visit the site during the trial, as well as communicate frequently via telephone and written communications.

10.2. Auditing

The sponsor's Quality Management Unit (or representative) may conduct trial site audits. Audits will include, but are not limited to, drug supply, presence of required documents, the informed consent process, and comparison of eCRFs with source documents. The investigator agrees to participate with audits.

Regulatory authorities may inspect the investigator site during or after the trial. The investigator will cooperate with such inspections and will contact the sponsor immediately if such an inspection occurs.

11. Ethics and Responsibility

This trial must be conducted in compliance with the protocol, the ICH GCP guideline, and applicable local laws and regulatory requirements. Each trial site will seek approval by an IRB or IEC according to regional requirements. The IRB/IEC will evaluate the ethical, scientific, and medical appropriateness of the trial. Further, in preparing and handling eCRFs, the investigator, subinvestigator, and their staff will take measures to ensure adequate care in protecting subject privacy. To this end, a subject number and subject identification code will be used to identify each subject.

Financial aspects, subject insurance and the publication policy for the trial will be documented in the agreement between the sponsor and the investigator.

Protocol 331-12-283

12. Confidentiality

All information generated in this trial will be considered confidential and will not be disclosed to anyone not directly concerned with the trial without the sponsor's prior written permission. Subject confidentiality requirements of the region(s) where the trial is conducted will be met. However, authorized regulatory officials and sponsor personnel (or their representatives) will be allowed full access to inspect and copy the records. All IMPs, subject bodily fluids, and/or other materials collected shall be used solely in accordance with this protocol, unless otherwise agreed to in writing by the sponsor.

Subjects will be identified only by initials and unique subject numbers in eCRFs. Per country regulations, if subject initials cannot be collected, another unique identifier will be used. Their full names may, however, be made known to a regulatory agency or other authorized officials if necessary.

13. Amendment Policy

The investigator will not make any changes to this protocol without the sponsor's prior written consent and subsequent approval by the IRB/IEC. Any permanent change to the protocol, whether an overall change or a change for specific trial site(s), must be handled as a protocol amendment. Any amendment will be written by the sponsor. Each amendment will be submitted to the IRB/IEC. Except for "administrative" or "nonsubstantial" amendments, investigators will wait for IRB/IEC approval of the amended protocol before implementing the change(s). Administrative amendments are defined as having no effect on the safety of subjects, conduct or management of the trial, trial design, or the quality or safety of IMP(s) used in the trial. A protocol change intended to eliminate an apparent immediate hazard to subjects should be implemented immediately, followed by IRB/IEC notification within 5 working days. The sponsor will submit protocol amendments to the applicable regulatory agencies.

When the IRB/IEC, investigators, and/or the sponsor conclude that the protocol amendment substantially alters the trial design and/or increases the potential risk to the subject, the currently approved written ICF will require similar modification. In such cases, repeat informed consent will be obtained before expecting continued participation.

Protocol 331-12-283

14. References

- ¹ Small GW, Rabins PV, Barry PP, Buckholtz NS, DeKosky ST, Ferris SH, et al. Diagnosis and treatment of Alzheimer disease and related disorders: consensus statement of the American Association for Geriatric Psychiatry, the Alzheimer's Association, and the American Geriatrics Society. *JAMA*. 1997;278(16):1363-71.
- ² Kaplan HI, Sadock BJ. Synopsis of psychiatry. 10th ed. Philadelphia: Lippincott Williams & Wilkins; 2007. p. 329.
- ³ Evans DA, Funkenstein H, Albert MS, Schen PA, Cook NR, Chown MJ, et al. Prevalence of Alzheimer's disease in a community population of older persons: higher than previously reported. *JAMA*. 1989;262(18):2551-6.
- ⁴ Losonczy KG, White LR, Brock DB. Prevalence and correlates of dementia: survey of the last days of life. *Public Health Rep*. 1998;113(3):273-80.
- ⁵ Costa PT Jr, Williams TF, Somerfield M, et al. Clinical Practice Guideline Number 19: Recognition and Initial Assessment of Alzheimer's Disease and Related Dementias. Rockville, MD: US Dept Health Human Services, Agency for Health Care Policy and Research; 1996. AHCPR publication 97-0702.

Appendix 3 Criteria for Identifying Laboratory Values of Potential Clinical Relevance

Laboratory Tests	Criteria
Chemistry	
AST (SGOT)	≥ 3 x ULN
ALT (SGPT)	≥ 3 x ULN
Alkaline phosphatase	≥ 3 x ULN
Lactate dehydrogenase	≥ 3 x ULN
Blood urea nitrogen	≥ 30 mg/dL
Creatinine	≥ 2.0 mg/dL
Uric acid	
Men	≥ 10.5 mg/dL
Women	≥ 8.5 mg/dL
Bilirubin (total)	≥ 2.0 mg/dL
Creatine phosphokinase	> 3 x ULN
Prolactin	> ULN
Hematology	
Hematocrit	
Men	≤ 37 % and decrease of ≥ 3 percentage points from baseline
Women	≤ 32 % and decrease of ≥ 3 percentage points from baseline
Hemoglobin	
Men	≤ 11.5 g/dL
Women	≤ 9.5 g/dL
WBC count	≤ 2,800 mm ³ or ≥ 16,000 mm ³
Eosinophils	≥ 10%
Neutrophils	≤ 15%
Absolute neutrophil count	≤ 1,500/mm ³
Platelet count	≤ 75,000/mm ³ or ≥ 700,000/mm ³
Urinalysis	
Protein	Increase of ≥ 2 units
Glucose	Increase of ≥ 2 units
Casts	Increase of ≥ 2 units
Additional Criteria	
Chloride	≤ 90 mEq/L or ≥ 118 mEq/L
Potassium	≤ 2.5 mEq/L or ≥ 6.5 mEq/L
Sodium	≤ 126 mEq/L or ≥ 156 mEq/L
Calcium	≤ 8.2 mg/dL or ≥ 12 mg/dL
Glucose	
Fasting	≥ 100 mg/dL
Non-fasting	≥ 200 mg/dL
Total cholesterol, fasting	≥ 240 mg/dL
LDL cholesterol, fasting	≥ 160 mg/dL
HDL cholesterol, fasting	
Men	< 40 mg/dL
Women	< 50 mg/dL
Triglycerides, fasting	≥ 150 mg/dL

ULN = upper limit of normal

Protocol 331-12-283

Appendix 4 Criteria for Identifying Vital Signs of Potential Clinical Relevance

Variable	Criterion Value ^a	Change Relative to Baseline ^a
Heart rate ^b	> 120 bpm	≥ 15 bpm increase
	< 50 bpm	≥ 15 bpm decrease
Systolic blood pressure ^b	> 180 mmHg	≥ 20 mmHg increase
	< 90 mmHg	≥ 20 mmHg decrease
Diastolic blood pressure ^b	> 105 mmHg	≥ 15 mmHg increase
	< 50 mmHg	≥ 15 mmHg decrease
Orthostatic hypotension	≥ 20 mmHg decrease in systolic blood pressure and a ≥ 25 bpm increase in heart rate from supine to sitting/standing	Not applicable (baseline status not considered)
Weight	–	≥ 7% increase
		≥ 7% decrease

^a In order to be identified as potentially clinically relevant, an on-treatment value must meet the “Criterion Value” and also represent a change from the subject’s baseline value of at least the magnitude shown in the “Change Relative to Baseline” column.

^b As defined in “Supplementary Suggestions for Preparing an Integrated Summary of Safety Information in an Original New Drug Application Submission and for Organizing Information in Periodic Safety Updates,” FDA Division of Neuropharmacological Drug Products draft (2/27/87).

Protocol 331-12-283

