1.3. Known and Potential Risks and Benefits

Based on the Investigator's Brochure,¹⁶ combined data from the completed phase 1 clinical trials indicate that brexpiprazole is safe and well tolerated in healthy subjects at single oral doses of 0.2 to 6 mg and at multiple oral doses up to 2 mg/day. Data from the completed multiple-dose clinical trials indicate brexpiprazole is well tolerated at multiple oral doses up to 12 mg/day in subjects with schizophrenia or schizoaffective disorder; up to 4 mg/day when coadministered with marketed ADT in subjects with MDD; and up to 4 mg/day when coadministered with marketed stimulant therapy in subjects with ADHD.

Based on data from the 18 completed phase 1 clinical trials in healthy subjects or special populations (including healthy subjects from 2 phase 1 trials conducted in special populations) (15 in the US, 2 in Japan, and 1 in Korea), the most frequently reported TEAEs (incidence \geq 5% or more of all healthy subjects who received brexpiprazole and more than placebo, administered either alone or with another marketed drug) were:

- Healthy subjects (N = 15 trials conducted in the US): dizziness, headache, postural dizziness, nausea, somnolence, constipation, and diarrhoea
- Healthy subjects (N = 3 trials conducted in Japan and Korea): nausea, orthostatic hypotension, somnolence, and dizziness

By indication, the most frequently reported TEAEs (incidence \geq 5% or more of all subjects who received brexpiprazole and more than placebo, administered either alone or with another marketed therapy or drug (ie, ADT, stimulant therapy, or antibiotic) in completed phase 1, phase 1b, and/or phase 2 double-blind patient trials (excluding subjects enrolled in phase 2 open-label extension trials) conducted under US Investigation New Drug Applications (INDs) were:

- Schizophrenia or schizoaffective disorder (N = 4 trials): headache, anxiety, akathisia, nausea, increased weight, and dizziness

Protocol 331-12-283

- MDD (N = 3 trials): akathisia, increased weight, insomnia, upper respiratory tract infection, and nasopharyngitis
- ADHD (N = 2 trials): insomnia

In the single completed phase 1 trial in subjects with schizophrenia conducted in Japan, TEAEs reported in 3 or more subjects who received brexpiprazole (of 21 total subjects) were:

- Schizophrenia (N = 1 trial): increased serum prolactin and increased serum creatine phosphokinase

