8.	Subjects who currently have clinically significant neurological, hepatic, renal, metabolic, hematological, immunological, cardiovascular, pulmonary, gastrointestinal, or psychiatric disorders. Clinically significant cardiovascular disorders include uncontrolled atrial fibrillation, heart failure, or ischemic heart disease. Surrogates for uncontrolled cardiovascular disease would include recent (within the last 6 months) hospitalizations or procedures, such as percutaneous coronary intervention, coronary bypass surgery. 
Medical conditions that are minor or well-controlled may be considered acceptable if the condition does not expose the subject to an undue risk of a significant adverse event or interfere with assessments of safety or efficacy during the course of the trial. The medical monitor should be contacted in any instance where the investigator is uncertain regarding the stability of a subject's medical condition(s) and the potential impact of the condition(s) on trial participation.

Protocol 331-12-283

Table 3.4.3-1 Exclusion Criteria	
9.	Subjects with uncontrolled hypertension (DBP > 95 mmHg) or symptomatic hypotension, or orthostatic hypotension, which is defined as a decrease of ≥ 30 mmHg in SBP and/or a decrease of ≥ 20 mmHg in DBP within 3 minutes of standing compared to the previous supine blood pressure, OR development of symptoms. Abnormal vital signs results should be repeated to ensure reproducibility of the abnormality before excluding a subject based on the criteria noted above.

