3.7.4.3.3. Vital Signs

Vital sign measurements will include body weight, body temperature, systolic blood pressure (SBP), diastolic blood pressure (DBP), and heart rate. The following guidelines will aid in the standardization of body weight measurements:

- The same scale should be used to weigh a given subject each time, if possible.
- Scales should be calibrated and reliable; scales should be at zero just prior to each subject's weigh-in session.
- A subject should void prior to being weighed and be minimally clothed (ie, no shoes or heavy overgarments).
- Weight should be recorded before a subject's meal and at approximately the same time at each visit.

Blood pressure and heart rate measurements will be made in the supine, sitting, and standing positions. The supine measurements will be performed first, followed by sitting, and finally standing. Blood pressure and heart rate measurements in the supine position should be taken after the subject has been lying for at least 5 minutes. The sitting and standing measurements should be taken within 1 to 3 minutes of changing positions. Vital signs scheduled at the same visit as blood samples are to be completed before blood is drawn.

Subjects with uncontrolled hypertension (screening DBP > 95 mmHg in any position) or symptomatic hypotension are excluded from the trial as are subjects with orthostatic hypotension, which is defined as a decrease of ≥ 30 mmHg in SBP and/or a decrease of ≥ 20 mmHg in DBP within 3 minutes of standing compared to the previous supine blood pressure or development of symptoms (see [Table 3.7-1](#)). In addition, subjects should be excluded if they have any other vital sign measurement at screening that, in the investigator's judgment, is medically significant in that it would impact the safety of the subject or the interpretation of the trial results. However, any abnormal screening vital sign result(s) considered to be clinically significant should be repeated to confirm the finding(s) before excluding the subject from the trial. Refer to [Appendix 4](#) for a list of potentially clinically significant vital signs.

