10.	Propranolol ^e	For treatment of akathisia or tremor: 7-day washout For treatment of heart disease: allowed provided that the dose has been stable for 30 days prior to randomization and total dose does not exceed 60 mg/day	For treatment of akathisia or tremor: maximum dose of 20 mg, 3 times daily (total of 60 mg/day). For treatment of heart disease: may remain on stable pretrial doses as needed throughout the trial, as long as the total dose does not exceed 60 mg/day. Propranolol must not be administered within 12 hours prior to the efficacy and safety scales.
11.	Varenicline	7-day washout	Prohibited
12.	Medications to treat other medical conditions, such as hypertension, hypercholesterolemia, etc., and anti-platelet agents	Allowed provided that the dose has been stable for 30 days prior to randomization	Subject should remain on the same dose throughout the duration of the trial, except when medically indicated due to a change in the underlying medical condition.

Protocol 331-12-283

Table 4.1-1 List of Restricted and Prohibited Medications			
All other psychotropic agents not listed in the below table are prohibited and must be discontinued at least 24 hours before the first dose of IMP.			
	Medication	Prior to Randomization	During Double-Blind Treatment Period
13.	Nutritional supplements and nonprescription herbal preparations with CNS effects (eg, St. John's wort, omega-3 fatty acids, kava extracts, gamma-aminobutyric acid (GABA) supplements, etc)	7-day washout	Prohibited
14.	Cytochrome P450 2D6 isozyme (CYP2D6) inhibitors or CYP3A4 inhibitors and inducers (see Table 4.1-2)	7-day washout	Prohibited

^aUse of intramuscular benzodiazepines are prohibited throughout the trial. However, limited use of specific oral benzodiazepines is permitted during screening and during the first 4 weeks of the randomization phase (baseline to Week 4 visit) to treat agitation and/or insomnia (see [Table 4.1-3](#)).

^bBenzodiazepines must not be administered within 12 hours prior to scheduled efficacy and safety scales, including EPS scales. Investigators are encouraged to delay scale administration until 12 hours have elapsed, if at all possible. However, if delaying administration of efficacy and safety scales is not feasible, the scales should still be administered and the use of benzodiazepine documented, including a notation of the drug name, dose, and time of administration on the eCRF.

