7.6. Safety Analysis

Standard safety variables to be analyzed include AEs, clinical laboratory tests, vital signs, ECGs, body weight, waist circumference and physical examination. In addition, data from the following safety scales will be evaluated: MMSE score, CCI [REDACTED]

[REDACTED] Safety analysis will be conducted based on the Safety Sample defined in [Section 7.2](#). In general, baseline of a safety variable is defined as the last observation of the variable before taking the first dose of IMP, unless specified otherwise. Prospectively defined criteria will be used to identify potentially clinically relevant abnormal values for clinical laboratory tests, vital signs, ECGs, and body weight. Details of safety analysis will be provided in the SAP.

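### Appendix 4's orthostatic-hypotension flag needs a 25 bpm heart-rate rise and has no postural diastolic limb, so some falls that meet the protocol's own eligibility definition go unflagged

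*Protocol*

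**What the plan says.** The protocol defines orthostatic hypotension twice.

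- **Eligibility.** Exclusion criterion 9 (Section 3.4.3, Table 3.4.3-1), restated in Section 3.7.4.3.3, takes "a decrease of ≥ 30 mmHg in SBP and/or a decrease of ≥ 20 mmHg in DBP within 3 minutes of standing". The reference is the supine reading, and symptoms alone also suffice. It sets no heart-rate condition.
- **On treatment.** The orthostatic row of Appendix 4 takes "≥ 20 mmHg decrease in systolic blood pressure and a ≥ 25 bpm increase in heart rate from supine to sitting/standing". It has no diastolic limb and no symptom limb, and baseline status does not count. Footnote a shows that the table is meant for values on treatment: "In order to be identified as potentially clinically relevant, an on-treatment value must meet the" tabulated criterion.

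On reporting, Section 7.6 states: "Prospectively defined criteria will be used to identify potentially clinically relevant abnormal values for clinical laboratory tests, vital signs, ECGs, and body weight". Sections 3.5.6 and 7.6.3 add that the potentially clinically relevant vital-sign results will be summarised. Appendix 4 is the only list of vital-sign criteria in the protocol. Section 3.7.4.3.3 gives the eligibility definition and then refers the reader to Appendix 4, without saying why the two differ.

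**The concern.** In Appendix 4 the heart-rate rise is a required condition. A large postural fall in pressure with a modest rise in heart rate is therefore not counted, and neither is a purely diastolic fall of any size. The same finding would have kept the subject out of the trial at screening.

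This matters for this drug. Section 1.3 lists "nausea, orthostatic hypotension, somnolence, and dizziness" as the most frequent treatment-emergent events in the healthy-subject trials in Japan and Korea, and postural dizziness is on the US list. Section 1.1.2 suggests alpha-1 blockade as the mechanism of the blood-pressure fall seen in animals. Table 4.1-1 also permits propranolol up to 60 mg/day on treatment. A beta-blocker would be expected to damp the heart-rate rise that the flag needs, although the protocol does not say how many subjects will take it. At stake is whether the vital-sign summary gives a fair count of postural falls by arm.

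**Working it through.** The protocol states no figure to reproduce, so the check compares the two rules as written.

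**Rules**
- Eligibility, blood-pressure part: SBP fall ≥ 30 OR DBP fall ≥ 20 mmHg, supine to standing.
- Appendix 4 flag: SBP fall ≥ 20 mmHg AND heart-rate rise ≥ 25 bpm, supine to sitting or standing.

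**Single cases** (a supine-to-standing change)

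| SBP fall | DBP fall | HR rise | Eligibility definition | Appendix 4 flag |
|---|---|---|---|---|
| 40 | 10 | 10 | met | no |
| 30 | 10 | 24 | met | no |
| 10 | 25 | 30 | met | no |
| 35 | 22 | 5 | met | no |
| 20 | 10 | 25 | not met | yes |
| 29 | 19 | 30 | not met | yes |
| 30 | 20 | 25 | met | yes |

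Neither rule contains the other.

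**Do the other Appendix 4 rows close the gap?** Take a subject on treatment at 150/80 with heart rate 70 supine, and 110/58 with heart rate 80 standing. The standing baseline was 145/78.
- Postural change: SBP 150 − 110 = 40, DBP 80 − 58 = 22, heart rate 80 − 70 = 10. The eligibility definition is met. The flag is not, because 10 < 25.
- Low-SBP row (< 90 with a fall of ≥ 20 from baseline): the change is 145 − 110 = 35, but 110 is not below 90.
- Low-DBP row (< 50 with a fall of ≥ 15 from baseline): the change is 78 − 58 = 20, but 58 is not below 50.
- High heart-rate row (> 120): 80 does not meet it.

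No row is tripped.

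**Size, on assumptions only.** The protocol gives no distribution of postural changes. As an illustration, assume normal distributions:
- SBP fall: mean 5, SD 15.
- DBP fall: mean 0, SD 9, correlation 0.5 with the SBP fall.
- Heart-rate rise: mean 5, 10 or 15, SD 8, uncorrelated with the DBP fall.
- Correlation of SBP fall with heart-rate rise: −0.2, 0 or 0.3.

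With 500,000 simulated measurements per setting, about 5.6% meet the blood-pressure part of the eligibility definition. The share of those that Appendix 4 flags is:

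| Mean HR rise | corr −0.2 | corr 0 | corr 0.3 |
|---|---|---|---|
| 5 bpm | 0.1% | 0.5% | 2.3% |
| 10 bpm | 1.0% | 2.8% | 8.6% |
| 15 bpm | 4.4% | 9.4% | 21.9% |

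The flag also counts some measurements that miss the eligibility definition, so the total flagged is the fairer basis for an incidence table. It runs from 0.03% to 3.2% of measurements, against about 5.6%. At the most favourable setting that is 3.2 / 5.63 = 57% of the eligibility count. These are shares of single measurements. A subject has seven on-treatment visits (Day 3 and Weeks 2, 4, 6, 8, 10 and 12), so the share of subjects ever flagged can be higher. The protocol gives no within-subject correlation from which to compute it.

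**The case against.** **Entry limits and on-treatment flags serve different purposes.** They differ elsewhere too: DBP > 95 mmHg at entry against > 105 in Appendix 4, and AST or ALT > 2 × ULN at entry against ≥ 3 × ULN in Appendix 3. Section 3.8.3 says that meeting an exclusion criterion after randomisation does not force discontinuation. This stands. The mismatch is not an error of conduct, and a reader should not infer that one definition is wrong. The orthostatic case differs in kind, however: DBP and AST/ALT are the same measure at another threshold, whereas here a limb is dropped and a different variable becomes a required condition.

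**The flag is not simply narrower.** Its systolic threshold is 20 rather than 30 mmHg, and it counts sitting as well as standing. This also stands, and it is why the point is one of rules that do not nest.

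**One row is not the whole safety display.** Section 7.6.1 tabulates treatment-emergent events, Section 7.6.3 summarises change from baseline in vital signs, and a data monitoring committee reviews safety. A reader might infer that flagged incidence will be near zero in every arm, or that the summary will show no orthostatic effect whatever the drug does. The documents do not support either reading, given these other displays and the unknown heart-rate distribution. The backstops are nevertheless partial. Section 5.2 elicits events by asking the subject how they have felt, in a population with MMSE 5 to 22, and change from baseline is not a supine-to-standing difference.

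**The prior signal is mixed.** Section 1.3 also reports no consistent, clinically relevant change in blood pressure or heart rate in the completed phase 1 and 2 trials in depression and schizophrenia, and the alpha-1 mechanism is nonclinical. This tempers the concern without removing it.

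**The statistical analysis plan may set its own criteria.** Section 7.6 defers details to it and does not name Appendix 4, so use of Appendix 4 for the tables is an inference, though footnote a makes it a natural one. The protocol itself nevertheless states this on-treatment rule.

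**Conclusion.** The point holds as a limited one. Under one name the protocol carries two definitions that overlap without nesting, and it does not explain the difference. The Appendix 4 criterion leaves unflagged any large postural fall with a heart-rate rise under 25 bpm and any isolated diastolic fall, and its absolute-value rows need not catch them. If Appendix 4 governs the tables, the vital-sign summary is likely to under-count orthostatic falls relative to the trial's own eligibility definition.

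The size cannot be derived from the protocol. The range of roughly 0.1% to 22% caught rests wholly on the assumed means, SDs and correlations, and applies to a single measurement. A reader might take it as showing that more than nine in ten affected subjects are missed. It does not: the upper end is well above one in ten, and the per-subject figure over seven visits is unknown. The rule comparison and the worked cases need none of these assumptions.

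**What to change.** Reconcile Appendix 4 with criterion 9 and Section 3.7.4.3.3 for reporting purposes. Keep the existing Appendix 4 criterion as it is. Add to Appendix 4 and to the vital-sign tables, by arm and visit:

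- a row for the blood-pressure part of the eligibility definition (SBP fall ≥ 30 and/or DBP fall ≥ 20 mmHg, supine to standing);
- a separate row for the heart-rate rise of ≥ 25 bpm, so that it can be read on its own.

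Add a sentence saying that the two definitions serve different purposes and why they differ.

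Nothing is removed, neither definition is declared the right one, and no eligibility, dosing or withdrawal rule changes. Supine, sitting and standing blood pressure and heart rate are already measured at every clinic visit from screening to Week 12/ET, so no new data are needed. The cost is one or two table rows and a higher reported incidence of orthostatic falls.
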